# Adults:

ECG interval	Categorical outlier criteria
QTcF	Treatment-emergent value of > 450 and ≤ 480 ms when not present at baseline (new onset)
	Treatment-emergent value of > 480 and ≤ 500 ms when not present at baseline (new onset)
	Treatment-emergent value of > 500 ms when not present at baseline (new onset)
	Increase of QTcF from baseline of > 30 and ≤ 60 ms
	Increase of QTcF from baseline > 60 ms
PR	Increase of PR from baseline > 25% resulting in PR > 200 ms
QRS	Increase of QRS from baseline > 25% resulting in QRS > 120 ms
HR	Decrease of HR from baseline > 25% resulting in HR < 50 bpm
	Increase of HR from baseline > 25% resulting in HR > 100 bpm

# **Children and Adolescents:**

ECG interval	Categorical outlier criteria
QTcF	Treatment-emergent value of > 450 and ≤ 480 ms when not present at baseline (new onset)
	Treatment-emergent value of > 480 and ≤ 500 ms when not present at baseline (new onset)
	Treatment-emergent value of > 500 ms when not present at baseline (new onset)
	Increase of QTcF from baseline of > 30 and ≤ 60 ms
	Increase of QTcF from baseline > 60 ms
PR	Increase of PR from baseline > 25% resulting in
	PR > 200 ms :- Adolescents (≥ 12 and < 18 years of age)
	PR > 180 ms :- Children (≥ 6 and < 12years of age)
QRS	Increase of QRS from baseline > 25% resulting in
	QRS > 110 ms :- Adolescents (≥ 12 and < 18 years of age)
	QRS > 100 ms :- Children (≥ 6 and < 12years of age)
HR	Decrease of HR from baseline > 25% resulting in
	HR < 50 bpm or HR > 100 bpm :- Adolescents (≥ 12 and < 18 years of age)

ECG interval	Categorical outlier criteria								
	HR < 60 bpm or HR > 120 bpm :- Children (≥ 6 and < 12years of age)								
	Increase of HR from baseline > 25% resulting in								
	HR < 50 bpm or HR > 100 bpm :- Adolescents (≥ 12 and < 18 years of age)								
	HR < 60 bpm or HR > 120 bpm :- Children (≥ 6 and < 12years of age)								

# 12.5. Physical Examination

A Physical examination will be performed at every visit. This will include physical examination of the following body areas and systems: Head, Eyes, Ears, Nose, Mouth, Throat, Neck (including Thyroid); Thorax; Abdomen; Urogenital; Extremities; Neurological; Skin and Mucosae; and Other.

A physical exam is optional at unscheduled visits, per the investigator's discretion.

The Physical examination results will be summarized at each visit by treatment group. All physical examination data will be presented in a listing.

### 12.6. Columbia Suicide Severity Rating Scale (C-SSRS)

The C-SSRS is a low burden (approximately 5 minutes for completion) instrument to assess both suicidal behavior and ideation. The scale is appropriate for subjects from age 6 through to an elderly population.

The number and percentage of subjects with suicidal behavior and ideation will be summarized by treatment group at all Visits except the 30-day Follow-up visit and all questionnaire data will be displayed in a listing.

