| Central Urine Drug Screen | X | X | | X | X | X | X | X | X | X | X | X | X | X | X | X | |
| Local Urine Pregnancy Test ⁱ | X | X | | X | X | X | X | X | X | X | X | X | X | X | X | X | |
| Yale Global Tic Severity Scale | X | X | | X | X | X | X | X | X | X | X | X | X | X | X | | |

Confidential

Page 39 of 96

Protocol EBS-101-TD-301 Version 9.0, 05 March 2024

| | | | Open-Label | Stabilizatio | on Period | | | | | | | | | | | | |
|--|--|------------------------------|--|--|---|--|---------------------------------------|---------------------------------------|---|---|---|---|--|---|--------------------------------------|--|---|
| | Screening Period ^a | Titrati | ion Phase | W | tenance Pl eeks 4 to 1 y 29 up to 8 | 2 | | | Double-Bli | Week | mized Withous 12 to 24 85 to 169) | lrawal Perio | od | | | fety Follo Days 170 | |
| Visit/TC Study Day | Screening VISIT 1 Day -28 to -1 | Baseline VISIT 2 Day 1 | W 2 f Day 15 Telephone call only (±3d) | W4 / VISIT 3/ Day 29 (±3d) | W8 / VISIT 4 / Day 57 (±3d) | W 12 VISIT 5 Day 85 (±3d) | W13 / VISIT 6 / Day 92 (±3d) | W14 / VISIT 7 / Day 99 (±3d) | W15 / VISIT 8 / Day 106 (±3d) | W16 / VISIT 9 / Day 113 (±3d) | W18 / VISIT 10 / Day 127 (±3d) | W20 / VISIT 11 / Day 141 (±3d) | W22 / VISIT 12/ Day 155 (±3d) | W 24 VISIT 13 Day 169 or Relapse or ET (±3d) | 7 Day F/U VISIT 14 (±3d) | 14 Day F/U VISIT 15 (±3d) | 30 Day F/U ^f Telephone call only (±3d) |
| Clinical Global Impression – Tourette Syndrome Severity | X | X | | X | X | X | X | X | X | X | X | X | X | X | | | |
| Clinical Global Impression – Tourette Syndrome Improvement | | | | X | | X | X | X | X | X | X | X | X | X | | | |
| Caregiver Global Impression of Change ^h | | | | Х | | X | | | | | X | | | X | | | |
| Gilles de la Tourette Syndrome – Quality of Life Scale for Children and Adolescents ^h | | X | | 1 | | X | | | | | | | | X | | | |
| Gilles de la Tourette Syndrome – Quality of Life Scale ^g | | X | | | | X | | | | | | | | X | | | |
| Premonitory Urge for Tics Scale | | X | | X | | X | | | | | X | | | X | | | |
| Columbia Suicide Severity Rating Scale | X | X | X | X | X | X | X | X | X | X | X | X | X | X | X | X | |
| Children's Depression Rating Scale – Revised ^h | X | X | | X | X | X | X | X | X | X | | X | | X | | | |
| Pediatric Anxiety Rating Scale ^h | | X | | X | X | X | X | X | X | X | | X | | X | | | |

Confidential

Page 40 of 96

Protocol EBS-101-TD-301 Version 9.0, 05 March 2024

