12.1.1. Columbia Suicide Severity Rating Scale (C-SSRS)¹⁰

The C-SSRS¹⁰ is a low burden instrument to assess both suicidal behavior and ideation. Questions are phrased for use in an interview format. The Screening/Baseline version will be administered at Screening and the Since Last Visit version of the scale will be administered at all subsequent visits. The scale is appropriate for subjects from age 6 through to an elderly population.

The clinician interview time is approximately 10 minutes.

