During the R/WD period, subjects will return to the clinic every week for the first 4 weeks and every 2 weeks thereafter (Weeks 13, 14, 15, 16, 18, 20, 22 and 24) and efficacy and safety assessments will be conducted at each of these visits. Any subject meeting Relapse criteria, defined as the loss of  $\geq$  50% of the improvement experienced on the YGTSS-TTS from Baseline (Day 1) to the last visit of the open-label Stabilization period Week 12, or initiation of additional medications to treat symptoms of TD, or requirement of hospitalization for worsening symptoms of TD will be withdrawn from blinded study medication (ecopipam or placebo).

An interim analysis (IA) will be conducted by an independent data safety monitoring board (DSMB) after approximately 70% of Relapse events have accrued (34 Relapse events). For details, please refer to section 13.

Non-responders to ecopipam during the open-label Stabilization period at either Week 8 or Week 12, or Responders randomized to ecopipam who complete the R/WD period, or who meet Relapse criteria during the R/WD period, or any subjects who discontinue the study prematurely for any reason will be

This document is confidential.

SAP text Version: SAP text 3.0 6-Dec-2023

Controlled Document ID: 3903A.02, Effective Date 31-Aug-2020

tapered off ecopipam in decrements of 22.4-mg/day and will complete the Week 24/Relapse/ET visit. Subjects assigned to placebo will receive placebo taper down medication to preserve the blind.

Follow Up visits will be conducted in the clinic 7 and 14 days after the last dose of study medication. Subjects will also be contacted by telephone 30 days after the last dose of study medication to determine any adverse events, with the exception of subjects who roll into the open-label extension study EBS-101-TD-391 within 30 days of their last study drug.

Subjects who experience Relapse may be treated for their TD with medications recommended by the PI or referred back to their primary physician for treatment after completing Day 7 and 14 follow-up visits.

Responders to ecopipam who complete the R/WD period and who complete the Week 24/Relapse/ET visit and the Day 7 and 14 follow-up visits are eligible to enter into the long-term open-label study EBS-101-TD-391. Subjects who meet the criteria for Relapse and complete the Week 24/Relapse/ET visit and the Day 7 and 14 follow-up visits will have the opportunity to enter the long-term open-label study.

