# 12. Safety

The population used for safety analyses will be the Safety Set (SS). Safety will be assessed by monitoring and recording all adverse events (AEs) and Serious Adverse Events (SAEs) (all Visits), regular monitoring of hematology, blood chemistry, and urine values (Screening, Baseline, Week 12, Week 18 and Week 24 Completion or Relapse/Early Termination, and 7- and 14-day Follow Up visits). HbA1c will be measured at Baseline, Week 12 and at Week 24 Completion or Early Termination visits. Regular measurement of vital signs and the performance of a physical examination will occur at every visit. An ECG will be performed at Screening, Baseline and Weeks 4, 12, 18, and 24 after supine BP is collected and at the 7-day and 14-day Follow Up visits. An additional assessment will include the Columbia-Suicide Severity Rating Scale (C-SSRS) (all Visits except 30 day Follow up visit). The Screening/Baseline version will be administered at Screening and the Since Last Visit version of the scale will be administered at all subsequent visits. Additional safety outcomes (Baseline and Weeks 4, 8, 12, 13, 14, 15, 16, 18, 20, 22 and 24) will include the Children's Depression Rating Scale-Revised (CDRS-R), the Pediatric Anxiety Rating Scale (PARS), the Extrapyramidal Symptom Rating Scale (ESRS), the Swanson, Nolan, and Pelham (SNAP-IV-26) questionnaire, the Children's Yale-Brown Obsessive Compulsive Scale-II (CY-BOCS-II), the Patient Health Questionnaire-9 (PHQ-9), the Hamilton Rating Scale for Anxiety (HAM-A), the Conners' Adult ADHD Rating Scale (CAARS) and the Yale-Brown Obsessive-Compulsive Scale-II (Y-BOCS-II). The C-SSRS and ESRS will be administered to all age groups whereas PARS, SNAP-IV-26, CY-BOCS-II and CDRS-R will be applicable for only children and adolescent subjects. The Y-BOCS-II, PHQ-9, CAARS and HAM-A will be administered to only adult subjects (>=18 years of age).

All safety data will be summarized using the Safety Set according to the actual treatment.

Treatment-emergent adverse events (TEAEs) are defined as adverse events that are newly occurring or worsening after the first dose of study medication. The incidence of TEAEs will be summarized by treatment group, by severity and by relationship to study medication. Serious TEAEs and TEAEs leading to the study termination will be summarized by treatment group. Laboratory data, vital sign, physical examination, and ECG will be summarized by treatment and visit.

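### C-SSRS by-visit percentages mix recall windows of 28, 7 and 14 days, so they can fall up to about fourfold at Week 13 with no change in risk, and no total by arm over the withdrawal period is planned

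*SAP*

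**What the plan says.** Protocol 12.1.1 gives the Screening/Baseline form of the C-SSRS at Screening, after which "the Since Last Visit version of the scale will be administered at all subsequent visits". SAP 12 repeats this and sets collection as "Columbia-Suicide Severity Rating Scale (C-SSRS) (all Visits except 30 day Follow up visit". In the R/WD period, visits take place "every week for the first 4 weeks and every 2 weeks thereafter" (SAP 4.1).

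The only planned C-SSRS summary is in SAP 12.6: "The number and percentage of subjects with suicidal behavior and ideation will be summarized by treatment group at all Visits", with the 30-day call excepted and all responses listed. The section has no count of subjects positive at any time in a period, no worst level, no definition of new or worse, no rate per patient-time and no remark on unequal recall.

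Suicidality also appears among the adverse events of special interest (Protocol 12.2.1.3; SAP 12.1, item 18). The SAP tabulates AEs by milestone, including R/WD Weeks 13-16 and Weeks 17-24 (SAP 12; SAP 12.1, item 15).

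**The concern.** A by-visit percentage suits a scale with a fixed lookback. The YGTSS, PARS, HAM-A and ESRS look back one week and the PHQ-9 two weeks, whatever the gap between visits (Protocol 11.1.1 and 12.1.3 to 12.1.6). The C-SSRS lookback is the visit gap itself, and that gap changes at randomization, which is where a reader would look for an effect of withdrawal.

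Two things are at stake. First, the series may suggest that suicidality was higher on open-label drug and eased after Week 12 when nothing changed, or may soften a real rise across that boundary. Second, a rare outcome split over eight columns cannot be read as a total for each arm. Subjects may be positive at more than one visit, so the columns cannot be added to give subjects, and denominators shrink as relapsed subjects leave blinded treatment.

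**Working it through.** The documents state no C-SSRS ratio or expected rate, so there is no plan figure to reproduce. The check derives the windows and then asks how the percentage responds to them.

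**1. Recall windows** (Protocol Table 3, nominal days). Examples are "W8 / VISIT 4 / Day 57", "W 12 VISIT 5 Day 85" and "W13 / VISIT 6 / Day 92".

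| Visit | Days since previous C-SSRS |
|---|---|
| Weeks 2, 4 | 14 each |
| Week 8 | 57 − 29 = 28 |
| Week 12 | 85 − 57 = 28 |
| Week 13 | 92 − 85 = 7 |
| Weeks 14, 15, 16 | 7 each |
| Weeks 18, 20, 22, 24 | 14 each |

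The window shrinks by 28/7 = 4 at Week 13. From Week 18 it is 28/14 = 2 times shorter than at Week 12. With the ±3-day visit tolerance, individual intervals run from 22 to 34 days at Week 12 and from 1 to 13 days at Week 13.

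**2. Brief events at a constant rate.** P(w) = 1 − exp(−λw).

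For illustration set P(28) = 5%, the level at which ideation was reported over the treatment phase of PSY302 (Protocol 5.2.2). This is not an estimate for this trial. Then λ = −ln(0.95)/28 = 0.00183 per day, P(7) = 1.27% and P(14) = 2.53%. The falls from Week 12 are 3.92-fold and 1.97-fold. The Week 12 to Week 13 ratio is 3.98 at P(28) = 1%, 3.97 at 1.7%, 3.85 at 10% and 3.52 at 30%.

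**3. Episodes that last.** With mean episode length D days, P(w) = 1 − (1 − π)exp(−λw) and π = λD/(1 + λD), with λ set so that P(28) = 5%. The documents give no D, so a range is shown.

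| D (days) | P(7) | Ratio 28 to 7 days | Ratio 28 to 14 days |
|---|---|---|---|
| 1 | 1.40% | 3.56 | 1.91 |
| 3 | 1.64% | 3.05 | 1.80 |
| 7 | 2.03% | 2.47 | 1.65 |
| 14 | 2.52% | 1.98 | 1.49 |
| 28 | 3.14% | 1.59 | 1.33 |
| 56 | 3.76% | 1.33 | 1.20 |

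Alternatively, let a share c of Week 12 positives be chronic and positive at every visit, with the rest proportional to window length. The ratio is 1/[c + (1 − c)/4]: 4.0 at c = 0, 2.3 at 25%, 1.6 at 50% and 1.0 at 100%.

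**4. A real rise across the boundary.** In the model of step 2, doubling the rate in Week 13 gives 1 − exp(−2 × 7λ) = 2.53%, against 5.0% at Week 12. In the model of step 3, with the same prevalence at the start of both windows, Week 13 equals Week 12 only if 7λ_new = 28λ_old. The onset rate would have to quadruple to look flat, whatever D is.

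**5. Pooling.** Any positive rating over Weeks 13 to 16 covers 4 × 7 = 28 days, the same as Week 12. In step 2 this gives 1 − (1 − 0.0127)^4 = 5.0%. For subjects rated at all four visits the match in window length does not depend on persistence.

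**6. Follow-up by arm.** Planned relapse in children and adolescents is 49 × 0.65 = 31.9 on placebo and 49 × 0.34 = 16.7 on ecopipam. Relapsed subjects leave blinded treatment, so observed R/WD time should be shorter on placebo.

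**The case against.** The strongest reply is that the randomized comparison is sound. Both R/WD arms follow one schedule, so at any visit ecopipam and placebo have the same nominal recall. A doubling confined to the withdrawn arm would show as about 2% against 1% at each weekly visit if the background rate were 1% per week (1 − exp(−0.02) against 1 − exp(−0.01)). This stands. A reader might infer that the display biases the treatment contrast or would hide a withdrawal effect between arms, and the documents do not support that.

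It is also fair that SAP 12.6 plans no formal open-label versus R/WD comparison of the C-SSRS, and that such a comparison is affected by selection in any case. Only Responders are randomized, and subjects with a new yes to question 4 or 5 are discontinued (Protocol 7.1, 7.5, 8.3). That limits what any fix can deliver. It does not make the unlabelled series safe to read across.

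The AESI tables, the milestone AE tables and the listing are real mitigation, but partial. They count recorded AEs, and neither document requires a positive C-SSRS answer to be recorded as one. AESI timing runs from first ecopipam dose, not from randomization. A listing leaves the reader to do the counting.

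Finally, counts will be small. At an assumed 0.5% per week, 98 children and adolescents would give 98 × (1 − exp(−0.02)) = 1.9 positives at Week 12, and each arm of 49 would give 49 × (1 − exp(−0.005)) = 0.24 at each weekly visit. A fall across the boundary would then be within chance. But small counts per column are also the reason to total them: 12 weeks with full follow-up would give 49 × (1 − exp(−0.06)) = 2.9 subjects per arm.

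**Conclusion.** The point holds as a weakness of a descriptive safety display. It touches no hypothesis test, endpoint or decision rule.

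What is fixed by the schedule is the window: 28 days, then 7, then 14. A reader might infer that the percentages themselves must drop fourfold at withdrawal. The documents do not support this, because they give no episode length or persistence. With risk unchanged, the Week 12 to Week 13 ratio lies between 1 and about 4 at nominal visit days. About 4 is the ceiling, reached only for rare, brief events at a constant rate. From Week 18 the ceiling is 2.

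The distortion is confined to reading across visits and between periods. Separately, the plan gives no total of C-SSRS positives by arm over a period in which follow-up is expected to differ by arm. The AE-based tables do not fill that gap.

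**What to change.** In SAP 12.6, add a table for the open-label period and, by arm, for the R/WD period. Divide R/WD by the SAP's existing milestones: Weeks 13-16, which match the four weekly visits, and Weeks 17-24. Show:

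- the number and percentage of subjects with any suicidal ideation (with worst level) or any suicidal behavior that is new or worse relative to Screening/Baseline. State which pre-treatment rating is the reference, since the Screening and Baseline visits use different forms of the scale;
- a rate per patient-time, with time taken from the intervals that the ratings cover.

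Keep the by-visit table, with the recall length in each column heading. Add a note that open-label versus R/WD comparisons remain affected by selection at Week 12 and by discontinuation after a new yes to question 4 or 5.

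The cost is one or two extra tables and some programming. No new data and no change to conduct are needed.

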#### 12.7. Other Safety

#### 12.7.1. Children's Depression Rating Scale-Revised (CDRS-R)

The CDRS-R is a clinically validated rating scale designed to assess psychiatric signs and symptoms of depressions. Fourteen signs and symptoms are rated from 1 being least severe (no difficulties) to 7 most severe (severe clinical difficulties), and 3 signs and symptoms are rated from 1 being least severe (no difficulties) to 5 most severe (severe clinical difficulties). The domains include social withdrawal, sleep disturbance, excessive fatigue, suicide ideation etc., aligned with the DSM-IV criteria for childhood depression.

## Derived Variables and Statistical Analysis:

The raw summary score is the sum of all 17 items, ranging from 17 to 113. The score will be calculated only if all the questions are answered.

The raw summary score will be summarized by treatment group at Baseline and Weeks 4, 8, 12, 13, 14, 15, 16, 20, and 24 visits and all questionnaire data will be displayed in a listing.

A shift table (<40, >=40 and overall) will be provided for CDRS-R raw summary score to assess clinically meaningful changes from Baseline by visit for each treatment group.

### 12.7.2. Pediatric Anxiety Rating Scale (PARS)

The PARS is a clinician-rated instrument for assessing the severity of anxiety symptoms associated with common anxiety disorders and generalized anxiety in children and adolescents. The PARS has two sections: the symptom checklist and the severity items. The symptom checklist is used to determine the child's repertoire of symptoms during the past week.

### Derived Variables and Statistical Analysis:

The 7-severity item is used to determine severity of symptoms and the PARS total score. Each severity item is coded from zero (none) to 5 (most extreme). Not applicable is coded to 8 and does not know is coded to 9. The total score for the PARS is total of the 7 severity items without imputing missing values. The total score ranges from 0 to 35. Codes "8" and "9" are not included in the summation.

The total score will be summarized by treatment group at the Baseline and Weeks 4, 8, 12, 13, 14, 15, 16, 20, and 24 visits and all questionnaire data will be displayed in a listing.

### 12.7.3. Extrapyramidal Symptom Rating Scale (ESRS)

The ESRS is a clinician-reported instrument developed to assess four types of drug-induced movement disorders: Parkinsonism, akathisia, dystonia, and tardive dyskinesia. For the subjective examination (subscale I of ESRS) scoring is on a four-point scale (0 = absent; 1=mild; 2=Moderate; 3 = severe).

#### Derived Variables and Statistical Analysis:

The subtotal ESRS I (sum of all 7-items without imputing missing values) will be summarized by treatment group at the Baseline and Weeks 4, 8, 12, 13, 14, 15, 16, 18, 20, 22 and 24 visits and all questionnaire data will be displayed in a listing.

All ESRS scores >= 1 will be adjudicated by the CAC and for any ESRS score >=1, the CAC will assign relatedness to the study drug.

# 12.7.4. Swanson, Nolan and Pelham (SNAP-IV) questionnaire

The SNAP-IV-26 questionnaire is designed to assess ADHD core symptoms of inattention (items 1-9), hyperactivity/impulsivity (items 10-18), and symptoms of oppositional defiant disorder (ODD) (items 19-26) in children and adolescents 6-18 years of age. In this study, 18-year-olds are defined as adults and will complete the CAARS-S:S adult scale. All 26 items are rated on 4-point scale and the total score ranges from 0-78, with higher scores indicating greater severity.

The SNAP-IV is based on a 0 to 3 rating scale: Not at All = 0, Just A Little = 1, Quite A Bit = 2, and Very Much = 3.

#### Derived Variables and Statistical Analysis:

Subscale scores on the SNAP-IV are calculated by summing the scores on the items in the subset and dividing by the number of items in the subset. The score for any subset is expressed as the Average Rating-Per-Item. Missing values will not be imputed.

The subscale scores will be summarized by treatment group at the Baseline and Weeks 4, 8, 12, 13, 14, 15, 16, 20, and 24 visits and all questionnaire data will be displayed in a listing.

# 12.7.5. Children's Yale-Brown Obsessive Compulsive Scale-II (CY-BOCS-II)

The CY-BOCS-II is a reliable and valid scale to both determine severity of OCD and to monitor improvement during treatment. The scale is a clinician-rated, 10-item scale (5 items regarding severity and 5 items regarding obsessions) that includes questions about the amount of time spent on obsessions/compulsions, level of impairment or distress, and how much resistance and control subjects have over these thoughts. The 10 items are assessed on a 6-point scale with an overall score.

